## 6.4.6. Minnesota Nicotine Withdrawal Scale (MNWS)

The Minnesota Nicotine Withdrawal Scale (MNWS) is a self-report measure used to monitor symptoms of tobacco withdrawal. The MNWS will be administered by an Investigator or other individual that is suitably qualified by education or training on Day -1 and at 5 hours (±30 minutes) postdose on Days 1 to 14 as outlined in Table 3. The assessment on Day -1 should be completed at approximately the same time as the 5-hour postdose timepoint on dosing days. See APPENDIX 11 for a MNWS example.

## 6.4.7. Questionnaire on Smoking Urges – Brief version (QSU-Brief)

The Questionnaire on Smoking Urges – Brief version (QSU-Brief) is a self-report questionnaire used to measure cravings to smoke. The QSU-Brief will be administered by an Investigator or other individual that is suitably qualified by education or training on Day -1 and at 5 hours (±30 minutes) postdose on Days 1 to 14 as outlined in Table 3. The assessment on Day -1 should be completed at approximately the same time as the 5-hour postdose timepoint on dosing days. See APPENDIX 12 for a QSU-Brief example.

Altasciences Project Number: CNO-P5-319

#### 7. ADVERSE EVENTS DOCUMENTATION

#### 7.1. **Definitions**

An AE is defined as any untoward medical occurrence in a subject administered an investigational product and which does not necessarily have a causal relationship with the treatment. An AE can therefore be any unfavorable and unintended sign (including for example, a clinically significant abnormal clinical laboratory finding), symptom, or disease temporally associated with the use of an investigational product, whether or not related to the investigational product.

A suspected adverse reaction (SAR) is any AE for which there is a reasonable possibility the drug caused the AE. 'Reasonable possibility' means there is evidence to suggest a causal relationship between the drug and the AE. A suspected adverse reaction implies a lower degree of certainty about causality than adverse reaction, which means any AE caused by a drug.

### An AE may be:

- A new illness,
- Worsening of a concomitant illness,
- An effect of the study drug including comparator; it could be an abnormal clinical laboratory value as well as a significant shift from baseline within normal range which an investigator considers to be clinically important.

Surgical procedures themselves are not AEs. They are therapeutic measures for conditions that required surgery. The condition for which the surgery is required is an AE, if it occurs or is detected during the study period. Planned surgical measures permitted by the clinical study protocol and the conditions(s) leading to these measures are not AEs, if the condition(s) was (were) known before the start of study treatment. In the latter case, the condition should be reported as medical history.

A Serious Adverse Event (SAE) or reaction is any untoward medical occurrence that at any dose:

- Results in death,
- Is life-threatening,
- Requires inpatient hospitalization or prolongation of existing hospitalization,
- Results in persistent or significant disability or incapacity (defined as a substantial disruption of a person's ability to conduct normal life functions),
- Is a congenital anomaly or birth defect,
- Is an important medical event that may jeopardize the subject or may require intervention to prevent one of the other outcomes listed above (according to medical judgment of an investigator)

# 7.2. Severity Assessment

All AEs will be graded as mild, moderate, or severe according to the following definitions:

Altasciences Project Number: CNO-P5-319

Mild: Causing no limitation of usual activities; the subject may experience transient slight

discomfort

Moderate: Causing some limitation of usual activities; the subject may experience annoying

discomfort

Severe: Causing inability to carry out usual activities; the subject may experience intolerable

discomfort or pain

Every effort will be made to obtain an adequate evaluation of the severity.

## 7.3. Causality Assessment

An Investigator will determine the relationship of any AE to the study drug using the guidelines presented in Table 14.

Table 14 Adverse Event Relationship to Study Drug

Relationship to Drug	Comment
Definite	A clinical event, including laboratory test abnormality, occurring in a plausible time relationship to drug administration and which cannot be explained by concurrent disease or other drugs or chemicals. The response to withdrawal of the drug (de-challenge) should be clinically plausible. The event must be definitive pharmacologically or phenomenologically using a satisfactory rechallenge (the drug is readministered to determine if the same reaction occurs) procedure if necessary.
Probable	A clinical event, including laboratory test abnormality, occurring in a plausible time relationship to drug administration and which cannot be explained by concurrent disease or other drugs or chemicals. The response to withdrawal of the drug (de-challenge) should be clinically plausible.
Possible	A clinical event, including laboratory test abnormality, with a reasonable time sequence to the drug administration, but which could also be explained by concurrent disease or other drugs or chemicals. Information on drug withdrawal may be lacking or unclear.
Unlikely	A clinical event, including laboratory test abnormality, with a temporal relationship to drug administration which makes a causal relationship improbable and in which other drugs, chemicals or underlying disease provide plausible explanations.
Not related	Any event that does not meet the above criteria; there is sufficient information that etiology of the event is in no relation to the study drug.

## 7.4. Adverse Event Monitoring

For the purposes of this study, the monitoring period for AEs extends from the pretrial evaluation until the Follow-up Visit. From Screening to the first dose of the study, AEs will be recorded as screening events or as part of the medical history, as applicable. AEs occurring after initiation of study drug will be indicated as TEAEs in the clinical study report.

Altasciences Project Number: CNO-P5-319

Subjects will be questioned on their health status at the beginning of each study period and before each departure from the CRU. Open-ended questions will be asked.

During the study, all AEs spontaneously reported by the subject, observed by the clinical staff or elicited by general questioning will be recorded for all subjects and reported in the CRF.

If necessary, every effort will be made to obtain an adequate follow-up of the subjects. Should any subject choose to withdraw from the study, they will be advised of the safety precautions to be taken.

Any AE which remains unresolved as of the last visit will require an evaluation and follow-up until the AE has been resolved or a reasonable explanation for its persistence found, or is deemed mild and safely resolving.

In the case of AEs deemed related to the Investigational Product, every effort will be made to determine the final outcome.

It is an investigator's responsibility to ensure that subjects experiencing AEs receive appropriate follow-up treatment where required, and that every action is well documented.

Classification of AEs will be performed by System Organ Class (SOC) and Preferred Term (PT) using the Medical Dictionary for Regulatory Activities (MedDRA), version 23.0 or higher.

Concomitant medications will be coded using the World Health Organization drug dictionary (WHO-DDE March 2019 or later).

## 7.5. Reporting of Pregnancy

Pregnancy in a female study subject shall be reported to the Sponsor within 24 hours of the knowledge of its occurrence by an investigator or delegate (for pregnancies occurring during the course of the study or immediately following the end of the study). Because of the possibility the fetus/embryo could have been exposed to the study drug through the parent and for the subject's safety, the pregnancy will be followed up to determine its outcome, including spontaneous or voluntary termination, details of birth, presence or absence of any birth defects, congenital anomalies, or maternal and/or newborn complications.

Pregnancy that occurs within 4 weeks after the last drug administration in a female partner of a male study subject shall be reported to the Sponsor within 24 hours of the knowledge of its occurrence by the clinical site that such pregnancy occurred during the course of the study or right after. Because of the possibility that the fetus/embryo could have been exposed to the study drug through the parent and for the safety of the subject's female partner, the pregnancy will be followed up to determine its outcome, including spontaneous or voluntary termination, details of birth, presence or absence of any birth defects, congenital anomalies, or maternal and/or newborn complications.

The pregnancy will be recorded and reported by the CRU to the Sponsor. Pregnancy follow-up will also be properly recorded to ensure quality and completeness of the data belonging to the study drug and will include an assessment of the possible causal relation between the study drug and any pregnancy outcome. Any SAE experienced during pregnancy will be reported on an SAE Report Form.

Altasciences Project Number: CNO-P5-319

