#### 4.1. Inclusion Criteria

- 1. Provision of written informed consent prior to the initiation of any protocol-specific procedures
- 2. Stated willingness to comply with all study procedures and availability for the duration of the study
- 3. Healthy male or female subject  $\geq 18$  and  $\leq 55$  years of age
- 4. Body mass index (BMI)  $\geq 18.5 \text{ kg/m}^2$  and  $\leq 32.0 \text{ kg/m}^2$
- 5. Body weight  $\geq$  50.0 kg at Screening
- 6. A female subject must meet at least one of the following criteria:
  - a) Is of childbearing potential and agrees to use an acceptable contraceptive method. Acceptable contraceptive methods include:
    - Total abstinence, in accordance with the lifestyle of the subject, from at least 30 days prior to the first study drug administration through to at least 90 days after the last dose of the study drug
    - One of the following contraceptive methods, used in combination with a barrier method (e.g., a diaphragm, a cervical cap, or a condom), from at least 30 days prior to the first study drug administration through to at least 90 days after the last dose of the study drug:
      - Intrauterine device (with or without hormones)
      - Spermicide

Or

- b) Is of non-childbearing potential, defined as surgically sterile (i.e., has undergone complete hysterectomy, bilateral oophorectomy, or tubal ligation) or is in a postmenopausal state (i.e., at least 1 year without menses prior to the first study drug administration without an alternative medical condition and confirmed with a serum follicle-stimulating hormone [FSH] > 40 IU/L at Screening)
- 7. Male subjects, if not surgically sterilized, must agree to use adequate contraception and not donate sperm from the first admission to the CRU until 90 days after the last study drug administration. Adequate contraception for the male subject (and/or his female partner) includes the following:

Altasciences Project Number: CNO-P5-319

- Use of spermicide, hormonal contraceptives or an intrauterine device combined with at least one of the following forms of contraception: a diaphragm, a cervical cap, or a condom
- Double-barrier method

Total abstinence, in accordance with the lifestyle of the subject, from at least 30 days prior to the first study drug administration until 90 days after the last study drug administration, is also acceptable

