## 4.2. Exclusion Criteria

- 1. Female who is lactating
- 2. Female who is pregnant according to the pregnancy test at Screening or prior to the first study drug administration

Altasciences Project Number: CNO-P5-319

- 3. Female who is planning to become pregnant during this study or within 90 days after the last study drug administration
- 4. Male with female partner who is pregnant, lactating, or planning to become pregnant during this study or within 90 days after the last study drug administration
- 5. Poor venous access as determined by an Investigator at Screening
- 6. History of significant hypersensitivity to SBP-9330 or any related products (including excipients of the formulations) as well as severe hypersensitivity reactions (like angioedema) to any drugs
- 7. Presence of any medical condition that, in the opinion of an Investigator, poses an unacceptable risk to the subjects
- 8. Presence or history of significant gastrointestinal, liver or kidney disease, or surgery that may affect drug absorption
- 9. Evidence or history of clinically significant cardiovascular, pulmonary, hematologic, psychiatric (including mood and substance use disorders), neurological (including migraines, seizures, and epilepsy), endocrine, renal, hepatic, gastrointestinal, immunologic or dermatologic disease
- 10. History of malignancy within the past five years, except for successfully treated basal cell carcinoma of the skin
- 11. History of suicidal ideation or suicidal behaviour as per the C-SSRS questionnaire administered at Screening
- 12. Evidence or history of significant psychiatric disease or any DSM-5 disorder as assessed by the Mini International Neuropsychiatric Interview (M.I.N.I.) administered at Screening
- 13. Routine or chronic use of more than three grams of acetaminophen daily
- 14. Strenuous activity, sunbathing, and contact sports within 48 hours prior to (first) admission to the CRU
- 15. Current alcohol consumption exceeding two standard drinks per day on average (1 standard drink=10 grams of alcohol) for male subjects and one standard drink per day on average for female subjects
- 16. History of alcohol or drug (other than caffeine) use disorder within 12 months prior to Screening
- 17. Any clinically significant illness in the 28 days prior to the first study drug administration
- 18. QTcF interval (QT interval corrected for heart rate according to Fridericia) > 450 ms for males and > 470 ms for females at Screening or on Day -1

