## 4.4. Lifestyle and/or Dietary Requirements

- Subjects will be prohibited from consuming food or beverages containing grapefruit and/or pomelo for 14 days prior to the first study drug administration and during the study.
- Subjects will be prohibited from consuming alcohol for 48 hours prior to each admission to the CRU until discharge. Throughout the study, in case of any doubt about alcohol consumption, a test for alcohol may be performed if requested by an Investigator
- Subjects will be prohibited from consuming food or beverages containing xanthines (i.e., tea, coffee, cola drinks, energy drinks or chocolate) for 48 hours prior to each admission to the CRU until last discharge.
- Subjects will eat only the food provided by the CRU during confinement.
- Female subjects of childbearing potential will have to take appropriate measures to prevent pregnancy from at least 30 days prior to the first study drug administration,

Altasciences Project Number: CNO-P5-319

during the study and for at least 90 days after the last dose of the study drug, as described in Section 4.1. It is the participant's responsibility to notify the CRU if a pregnancy occurs from the end of their study participation until 90 days after the last dose of the study drug.

- Male subjects will be expected to use an acceptable contraceptive regimen and not to donate sperm from the first admission to the CRU, during the study, and until at least 90 days after the last study drug administration, as described in Section 4.1. Reporting for pregnancy in female partners is detailed in Section 7.5.
- For the Smoker cohorts, subjects will abstain from smoking tobacco cigarettes for at least 1 hour before and 2 hours after study drug administration. Subjects will also abstain from using nicotine-containing products other than tobacco cigarettes (e.g., pipes, cigars, e-cigarettes or vapes, nicotine topical patches, nicotine gum, or nicotine lozenges) or other tobacco products (cigars, cigarillos, pipes) during the study.

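### Partner-pregnancy reporting stops at 4 weeks after the last dose while the male precautions run to 90 days, and the female-subject reporting sentence has no 90-day window either

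*Protocol*

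**What the plan says.** Section 7.5 of the protocol has one paragraph for female subjects and one for female partners of male subjects.

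- **Partners.** The pregnancies to be reported to the sponsor are those meeting "Pregnancy that occurs within 4 weeks after the last drug administration in a female partner". The sentence closes with a looser phrase, that "such pregnancy occurred during the course of the study or right after". The same paragraph requires follow-up to outcome and gives the reason: "Because of the possibility that the fetus/embryo could have been exposed to the study drug through the parent".
- **Female subjects.** Reporting covers pregnancies during the study or directly after it ends. No number of days is given.

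The precautions for men run longer. Inclusion criterion 7 (Section 4.1) requires contraception of men who have not been sterilised, and over the same period they are to "not donate sperm from the first admission to the CRU until 90 days after the last study drug administration". Exclusion criterion 4 (Section 4.2) bars any "Male with female partner who is pregnant, lactating, or planning to become pregnant during this study or within 90 days after the last" dose. The male bullet in Section 4.4 repeats the rule, "until at least 90 days after the last study drug administration, as described in Section 4.1", and then refers the reader to Section 7.5 for partner pregnancies.

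The bullet for female subjects in Section 4.4 gives each woman the "responsibility to notify the CRU if a pregnancy occurs from the end of their study participation until 90 days after the last" administration. The male bullet contains no such sentence. The SAP says nothing on pregnancy reporting.

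**The concern.** The protocol treats the 90 days after the last dose as a period in which conception by a treated man should be prevented. If prevention fails after week 4, the protocol as written asks nobody to report the pregnancy or follow it to outcome, although the reason it gives for follow-up is possible exposure through the parent. No reason is given for stopping at 4 weeks.

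At stake is safety information. SBP-9330 has not been given to humans before (Section 1.2.3), so any pregnancy after exposure of the father would be among the first human data of that kind.

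The female side of Section 7.5 has a related defect. Section 4.4 asks women to notify the CRU until 90 days, but the site's own duty to report and follow up is not tied to those 90 days.

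**Working it through.** The plan states no figure to reproduce. The check compares the time windows and then gives a rough size.

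**1. Windows after the last dose**

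| Provision | Section | Runs to |
|---|---|---|
| Male contraception, no sperm donation | 4.1, inclusion 7 | 90 days |
| Partner not planning pregnancy | 4.2, exclusion 4 | 90 days |
| Male lifestyle rule | 4.4 | at least 90 days |
| Female subject notifies CRU | 4.4 | 90 days |
| Male subject notifies CRU of partner pregnancy | none stated | none stated |
| Site reports and follows partner pregnancy | 7.5 | 4 weeks |
| Site reports and follows female subject's pregnancy | 7.5 | directly after study end, no days given |

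**2. Length of the partner gap.** 4 × 7 = 28 days. 90 − 28 = 62 days, that is days 29 to 90. 62/90 = 69% of the calendar days.

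**3. Could scheduled contact close it?** The last visit is Day 8±1 after a Day 1 dose in Part A (for Cohort A3, counted within Period 2), and Day 21±1 after a Day 14 dose in Parts B and C. Both are 7±1, so 6 to 8 days after the last dose. Adverse event monitoring ends at that visit (Section 7.4). Later pregnancies reach the site only if someone reports them.

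**4. Expected partner pregnancies in the gap.** Formula: men × 62/365.25 × yearly rate.

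- Planned active subjects: 5×6 + 3×8 + 2×8 = 70. Section 4 aims for similar numbers of each sex, so about 35 men.
- All planned subjects: 40 + 30 + 20 = 90, so about 45 men. The Section 7.5 duty applies to any male subject, placebo included.
- Yearly rate: 1% to 5%. This is an assumption; the documents give no rate.

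35 × 62/365.25 = 5.94 person-years; × 0.01 = 0.06; × 0.05 = 0.30.

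45 × 62/365.25 = 7.64 person-years; × 0.01 = 0.08; × 0.05 = 0.38.

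Under a Poisson model with mean 0.38, the chance of no event is exp(−0.38) = 0.68, so zero is the most likely count even at the upper rate.

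**The case against.** **Precaution and reporting windows need not match.** This is fair. Nothing in the documents says they must be equal, and a sponsor may choose different lengths. The 4 weeks also limits when the pregnancy occurs, not when it is discovered: one that occurs by day 28 and comes to light on day 60 is still reportable. What remains is that the protocol gives no reason for the shorter window, and its own ground for follow-up does not lapse at day 28.

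**A reader might infer that 69% of the risk goes unwatched.** The documents do not support that. The figure counts calendar days, and the period closest to dosing is covered.

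**A reader might infer that women are fully covered to 90 days and only the men's side is deficient.** That is also wrong. The 90-day sentence in Section 4.4 binds the participant to tell the CRU. The site's duty in Section 7.5 has no 90-day figure for women. Correcting only the partner paragraph would leave the section lopsided.

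**A reader might infer that men have no duty to notify at all.** The protocol states none, but the consent form and site procedures are not visible and may contain one. The point is limited to the protocol text.

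**The visible reproductive data are reassuring.** Section 1.2.2 reports negative in vitro genotoxicity assays and no testicular toxicity in male rats dosed for 12 weeks at up to 300 mg/kg/day. This lowers the weight of the point, but the protocol does not cite these data as the reason for 4 weeks.

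**Conclusion.** The mismatch is real and stands in the current text. For days 29 to 90 the protocol imposes precautions on men but states no duty to report or follow up a partner pregnancy, and Section 4.4 points to no provision other than Section 7.5. The female-subject sentence in Section 7.5 also lacks a 90-day window.

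The practical weight is small. Expected partner pregnancies in the gap are well below one: about 0.06 to 0.30 among men on active drug, or 0.08 to 0.38 with placebo included. These figures rest on the assumed 1% to 5% per year and on half the subjects being men. They should not be read as upper or lower limits. The sex balance is only a goal, withdrawn subjects may be replaced, and optional cohorts may be added; on the other hand, nothing is deducted for sterilised, abstinent or unpartnered men.

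No endpoint, analysis, escalation or stopping rule depends on this. The gain is in safety follow-up only, so it is a desirable correction and not a necessary one.

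**What to change.** In Section 7.5, give the female-subject and the female-partner paragraphs the same window for reporting and follow-up: *during the study or within 90 days after the last drug administration*. Keep the 24-hour limit from site knowledge. In the partner paragraph, delete the closing clause that "such pregnancy occurred during the course of the study or right after". It is vague, and the new wording already covers pregnancies during the study.

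In the male bullet of Section 4.4, add that the participant is to tell the CRU of a partner's pregnancy during the study or until 90 days after the last dose, if the consent form does not already say so. Align the two documents either way.

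The cost is a few wording changes sent to the institutional review board (IRB) with the next amendment, with matching consent wording if needed. No visit or procedure is added. The downside is possibly a few late reports to follow to outcome.
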